3.5.3. Body Weight

Body weight will be measured at times specified in the SoA given in the protocol.

The baseline measurement is the predose measurement on Day 1 of Period 1.

3.5.4. Vital Signs

Supine blood pressure (BP), pulse rate (PR) and temperature will be measured at times specified in the SoA given in the protocol.

The baseline measurement is the latest predose measurement on Day 1 of Period 1.

3.5.5. Electrocardiograms

QT interval, QTcF, PR, QRS and heart rate (HR) will be recorded at each assessment time indicated in the SoA given in the protocol. QTcF will be derived using Fridericia’s heart rate correction formula:

$$\text{QTcF} = \text{QT} / (\text{RR})^{(1/3)} \text{ where RR} = 60/\text{HR} \text{ (if not provided)}$$

The baseline measurement is the latest measurement on Day 1 of Period 1.

3.5.6. Mental health

3.5.6.1. Columbia Suicide Severity Rating Scale (C-SSRS)

The C-SSRS is an interview-based rating scale to systematically assess suicidal ideation and suicidal behavior. The “baseline/screening” version of the C-SSRS will be administered at Screening and Day -1 in study. Participants who respond “yes” to Question 4 or 5 (indicating suicidal ideation), or to any suicidal behavioral question on the C-SSRS at

screening or Day -1 will not be permitted in the study (see CCI). The “since last visit” version of the C-SSRS will be administered at the time points specified in the SoA. The C-SSRS will be administered by study site staff who have completed training in its administration. Participants who have recurrent suicidal ideation or behavior during the study should be discontinued from the study and treated appropriately. If a study participant endorses a 4 or 5 on the ideation subscale or any behavioral item of the C-SSRS on 2 or more occasions and is confirmed to have active suicidal ideation or behavior on both occasions by a risk assessment conducted by a qualified MHP, then the participant should be discontinued from the study and treated appropriately.

3.5.6.2. Patient Health Questionnaire-9 (PHQ-9)

The PHQ-9 is a 9 item self-report scale for the assessment of depressive symptoms. The PHQ-9 will be completed by participants and reviewed by site staff at the pre-defined time points outlined in the SoA. A PHQ-9 score of ≥ 15 at Screening or Day -1 indicates clinically significant depression and serves as an exclusion criterion for this study (see section 5.2 of the protocol).

The PHQ-9 is a 9 item self-report scale for the assessment of depressive symptoms. The PHQ-9 will be completed by participants and reviewed by site staff at the pre-defined time points outlined in the SoA. The total score will be derived by adding the corresponding values of responses to each item. The total score ranges from 0 to 27, with the following interpretation:

Total Score	Depression Severity
1-4	Minimal depression
5-9	Mild depression
10-14	Moderate depression
15-19	Moderately severe depression
20-27	Severe depression

A participant with a postbaseline assessment with a score of ≥ 15 should be referred to a MHP.

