**Table 1. Study Schedule of Assessment**

Visit Identifier' Abbreviations used in this table may be found in Appendix 9 .	Screen	Period 1		Period 2	Period 3	F/U (Phone Call) 47 to 54 28-35 Days	ET	Notes
		-1 D-1	Ito5 D1 toD5	6to 10 D1 to D5	11 to 20 D1 to D10			
Study Day Days Relative to Day 1	D-28 to D-2							
HIV, HBsAg, HBcAb, HCV RNA, HCVAb	X							
C-SSRS and PHQ-9	X	X			X (D10)		X	
COVID-19 assessments		X						
 
See Section 8.3.5.
 

Study intervention administration PF-07081532			X(D1)	X(D1)	X(D4)			
 
See Table 2 and Table 3 for specifics.
 

Study intervention administration itra conazole					X (D1-9)			
 
See Table 3.
 

Study intervention administration cyclosporine				X(D1)				
 
See Table 2.
 

Pharmacokinetic blood sampling: PF-07081532			D1-5	D1-5	D4-10		X	
 
See blood sampling timepoints in Table 2 for Periods 1 and 2 and Table 3 for Period 3.
 

CCI [REDACTED]			[REDACTED]					[REDACTED]
CCI [REDACTED]			[REDACTED]					[REDACTED]

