#### **8.3.8.2. Patient Health Questionnaire-9 (PHQ-9)**

The PHQ-9 is a 9 item self-report scale for the assessment of depressive symptoms. The PHQ-9 will be completed by participants and reviewed by site staff at the pre-defined time points outlined in the [SoA](#). A PHQ-9 score of  $\geq 15$  at Screening or Day -1 indicates clinically significant depression and serves as an exclusion criterion for this study (see [Section 5.2](#)).

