#### **8.3.8.3. Referral to a Mental Health Professional**

A participant should be referred to a MHP for the following reasons:

- Response of "yes" to question 4 or 5, or on any suicidal behavioral question on the C-SSRS.
- A score of  $\geq 10$  on the PHQ-9.
- In the investigator's judgment a risk assessment or exclusion is required.

A clinically qualified MHP is an MHP with appropriate training in the assessment of suicide risk, according to local clinical practice standards and regulations, who would normally evaluate the risk for suicidal ideation and behavior in a patient.

Participants who have recurrent suicidal ideation or behavior during the study should be discontinued from the study and treated appropriately. If a study participant endorses a 4 or 5 on the ideation subscale or any behavioral item of the C-SSRS on 2 or more occasions and is confirmed to have active suicidal ideation or behavior on both occasions by a risk assessment conducted by a qualified MHP, then the participant should be discontinued from the study and treated appropriately.

Participants who meet criteria for referral to a MHP but refuse evaluation and/or treatment by a MHP, must be assessed by the investigator to determine if the participant should be discontinued from dosing or from the study.

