#### 9.3.2.2. Mental Health

Assessment of mental health as determined by C-SSRS and PHQ-9. Details will be provided in the SAP.

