2. INTRODUCTION

GLP-1 is a neuroendocrine hormone that is predominantly released from the small intestine in response to food intake. GLP-1 activation of the GLP-1R stimulates insulin release, inhibits glucagon secretion in a glucose-dependent manner, and delays gastric emptying. In addition, GLP-1 has been shown to increase satiety and suppress food intake.

PF-07081532 is an orally administered, potent and selective GLP-1R agonist in development as adjunct to diet and exercise, to improve glycemic control in T2DM, and for chronic weight management in a population that is overweight with co-morbidities or who have obesity.

This statistical analysis plan (SAP) provides the detailed methodology for summary and statistical analyses of the data collected in Study C3991041.

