6.5.6. Mental Health

C-SSRS and PHQ-9 data will be listed.

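### Two safety thresholds are misstated: PHQ-9 referral is 15 in the SAP but 10 in the protocol, and the protocol pairs 54 mg/dL glucose with 2.7 mmol/L

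*SAP*

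**What the plan says.** **PHQ-9 referral**

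- Protocol 8.3.8.3 opens its list with "A participant should be referred to a MHP for the following reasons". The list contains a qualifying C-SSRS response, a PHQ-9 score of 10 or more, and cases where, in the investigator's "judgment a risk assessment or exclusion is required". The PHQ-9 item carries no limit on timing.
- Protocol 8.3.8.2 uses 15 for a different purpose. A score of 15 or more at Screening or Day -1 "indicates clinically significant depression and serves as an exclusion criterion for this study". Exclusion criterion 18 in section 5.2 agrees.
- SAP 3.5.6.2 repeats that exclusion rule, gives a severity table in which 10-14 is moderate depression, and ends with "A participant with a postbaseline assessment with a score of ≥ 15 should be referred to a MHP".
- Protocol 9.3.2.2 says of mental health: "Details will be provided in the SAP". SAP 6.5.6 plans only this: "C-SSRS and PHQ-9 data will be listed".
- The "C-SSRS and PHQ-9" row of protocol Table 1 has one in-study postbaseline time, Period 3 Day 10 (the day of discharge), plus early termination.

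**Severe hypoglycemia**

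- Protocol 8.3.6.1 defines a hypoglycemic adverse event by glucose below 70 mg/dL, given as 3.9 mmol/L.
- A severe grade needs three criteria together. The third, when glucose was measured, is a value of 54 mg/dL or less, with 2.7 mmol/L in parentheses.

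**The concern.** Each item is a decision limit that appears with two values.

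For the PHQ-9, the two documents name different scores for the same action. The SAP sentence does not forbid referral at 10 to 14, but as a restatement of the protocol rule it is incomplete. Referral is part of the protocol's mitigation for suicidal ideation and behavior (section 2.3.1). The only planned postbaseline PHQ-9 falls on the day of discharge or at early termination, and the later follow-up is a telephone call. No later scheduled PHQ-9 would catch a missed referral.

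For glucose, an event that already meets the first two severe criteria could be graded severe, or mild or moderate, depending only on which unit is read.

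**Working it through.** **PHQ-9.** The protocol's referral range is 10 to 27, which is 27 − 10 + 1 = 18 scores. The SAP's is 15 to 27, which is 27 − 15 + 1 = 13 scores. The difference is 18 − 13 = 5 scores, 10 to 14, the band that the SAP's own table calls moderate depression. With one postbaseline assessment per participant and about 16 enrolled, about 16 assessments are exposed to the discrepancy, or somewhat more if participants are replaced. No planned output uses the referral score.

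**Glucose.** The inputs are the two pairs in protocol 8.3.6.1: 70 mg/dL with 3.9 mmol/L, and 54 mg/dL with 2.7 mmol/L.

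1. Conversion factor from the first pair: 70 / 3.9 = 17.95 mg/dL per mmol/L.
2. Factor from the second pair: 54 / 2.7 = 20.0. On that factor, 70 mg/dL would be 70 / 20.0 = 3.5 mmol/L rather than 3.9. The two pairs cannot both be right.
3. On the first factor, 54 / 17.95 = 3.01 mmol/L, and 2.7 × 17.95 = 48.5 mg/dL.
4. Could rounding explain it? If 3.9 stands for 3.85 to 3.95, the factor lies between 70 / 3.95 = 17.72 and 70 / 3.85 = 18.18. Then 54 mg/dL lies between 54 / 18.18 = 2.97 and 54 / 17.72 = 3.05 mmol/L.
5. If 2.7 also stands for 2.65 to 2.75, it corresponds to between 2.65 × 17.72 = 47.0 and 2.75 × 18.18 = 50.0 mg/dL. The upper end is still 4 mg/dL short of 54, so rounding does not close the gap.

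A measured value above about 48.5 and up to 54 mg/dL therefore meets the third criterion in mg/dL and fails it in mmol/L.

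**Which unit was meant?** The documents do not say. Outside 8.3.6.1, the fasting-glucose limit in exclusion criterion 23 (126) and all three limits in section 8.3.6.2 (each 70) are in mg/dL only. Within 8.3.6.1, mg/dL comes first and mmol/L is in parentheses. This supports mg/dL as the intended unit but does not settle it.

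**The case against.** The other side accepts both textual differences and argues that they are editorial.

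- **Referral is a site action under the protocol.** Section 8.3.8.3 is complete and also allows referral on the investigator's judgment. The SAP, by its own introduction, "provides the detailed methodology for summary and statistical analyses of the data collected in Study C3991041". A site that follows the protocol refers every participant scoring 10 to 14, so nobody is handled differently. This stands, and it makes the PHQ-9 item the weaker of the two.
- **The pointer in protocol 9.3.2.2 concerns analysis, not referral.** It sits under Safety Analyses. This also largely stands. The pointer sends a reader to the SAP for mental-health details, where the wrong score is found, but it does not give the SAP authority over referral.
- **The glucose error rarely matters.** All three criteria are required, diabetes is excluded, anti-diabetic drugs are prohibited, and section 8.3.6 does not expect hypoglycemia. Any such event is below 70 mg/dL and so counts as a hypoglycemic event on either reading; only its severity grade can change. The SAP names no separate hypoglycemia analysis. This stands as a limit on size.
- **The two items are unrelated** and do not add up to something larger. That is correct, and each is judged on its own here.

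None of this makes either text right. Both are limits on which someone may act, and each correction is a single figure.

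**Conclusion.** Both discrepancies hold, and both are low priority.

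The SAP's postbaseline referral score of 15 does not match the protocol's 10 and leaves five scores unnamed. Because the protocol governs conduct and the data are only listed, no planned table changes.

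The 54 mg/dL and 2.7 mmol/L pair is wrong by the section's own conversion. It leaves measured values above about 48.5 and up to 54 mg/dL with an ambiguous severe grade, for events that already meet the other two criteria. This is the stronger item because nothing elsewhere in the plan resolves it. That 54 mg/dL is the correct half of the pair is an assumption, supported by the mg/dL-only limits elsewhere.

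The PK analyses and sample size are untouched.

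**What to change.** 1. **SAP 3.5.6.2:** change the postbaseline referral score to 10 or more, matching protocol 8.3.8.3, and keep 15 only as the Screening and Day -1 exclusion cut-off. Replacing the sentence with a cross-reference to 8.3.8.3 would serve equally well. This is a one-line edit at the next SAP version.
2. **Protocol 8.3.6.1, third severe criterion:** have the sponsor confirm the intended unit against its source. If it is mg/dL, as assumed here, write 54 mg/dL (3.0 mmol/L). If 2.7 mmol/L was intended, the mg/dL figure should be about 48.5 (47.0 to 50.0 allowing for rounding). A clarification letter or the next amendment is enough, with IRB/EC approval as applicable under section 10.1.1.

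Neither item justifies an amendment of its own.

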4. ANALYSIS SETS (POPULATIONS FOR ANALYSIS)

For purposes of analysis, the following analysis sets are defined:

Participant Analysis Set	Description
Enrolled	“Enrolled” means a participant’s, or their legally authorized representative’s, agreement to participate in a clinical study following completion of the informed consent process and assignment to study intervention. A participant will be considered enrolled if the informed consent is not withdrawn prior to participating in any study activity after screening. Potential participants who are screened for the purpose of determining eligibility for the study, but do not participate in

Participant Analysis Set	Description
	the study, are not considered enrolled, unless otherwise specified by the protocol.
Safety analysis set	All participants randomly assigned to study intervention and who take at least 1 dose of study intervention. Participants will be analyzed according to the product they actually received.
PK concentration set	All participants who take at least 1 dose of study intervention and in whom at least 1 concentration value is reported.
PK parameter set	All participants who take at least 1 dose of study intervention and in whom at least 1 of the PK parameters of primary interest are reported.

5. GENERAL METHODOLOGY AND CONVENTIONS

Final analysis will be performed after study participant data set release following last participant last visit.

5.1. Hypotheses and Decision Rules

No statistical hypothesis will be tested in this study.

5.2. General Methods

5.2.1. Analyses for Binary/Categorical Endpoints

For binary or categorical variables, number of participants, and numbers and percentages of participants meeting the categorical criteria will be presented in accordance with the Clinical Data Interchange Standards Consortium and Pfizer Standards (CaPS).

5.2.2. Analyses for Continuous Endpoints

For continuous variables, the data will be summarized using the number of participants, mean, median, standard deviation (SD), minimum, and maximum in accordance with the CaPS. For appropriate PK parameters, geometric mean and geometric coefficient of variation (%CV) will also be summarized.

5.3. Methods to Manage Missing Data

5.3.1. Pharmacokinetic Data

Methods to handle missing PK data are described below.

Concentrations Below the Limit of Quantification:

In all data presentations (except listings), concentrations below the limit of quantification (BLQ) will be set to zero. (In listings, BLQ values will be reported as “<LLQ”, where LLQ will be replaced with the value for the lower limit of quantification.).

Deviations, Missing Concentrations and Anomalous Values:

In summary tables and plots of median profiles, statistics will be calculated having set concentrations to missing if 1 of the following cases is true:

1. A concentration has been collected as ND (ie, not done) or NS (ie, no sample).
2. A deviation in sampling time is of sufficient concern or a concentration has been flagged anomalous by the pharmacokineticist.

Note that summary statistics will not be presented at a particular time point if more than 50% of the data are missing.

An anomalous concentration value is one that, after verification of bioanalytical validity, is grossly inconsistent with other concentration data from the same individual or from other participants. For example, a BLQ concentration that is between quantifiable values from the same dose is considered as anomalous. Anomalous concentration values may be excluded from PK analysis at the discretion of the PK analyst.

PK Parameters:

Actual PK sampling times will be used in the derivation of PK parameters. If a PK parameter cannot be derived from a participant's concentration data, the parameter will be coded as NC (ie, not calculated). (Note that NC values will not be generated beyond the day that a participant discontinues).

In summary tables, statistics will not be presented for a particular treatment group if more than 50% of the data are NC. For statistical analyses, PK parameters coded as NC will also be set to missing.

If an individual participant has a known biased estimate of a PK parameter (due for example to dosing error or an unexpected event, such as vomiting, before all the compound is adequately absorbed from the gastrointestinal tract), this will be footnoted in summary tables and will not be included in the calculation of summary statistics or statistical analyses. For instance, if a participant has a vomiting event post dose that is within a duration of time that is 2-times the derived median T_{max} for the population for the administered treatment, then the pharmacokineticist should consider the exclusion of the PK concentration data collected following the initial vomiting event in that treatment period and the PK parameter data reported for that treatment period from the datasets used to calculate summary statistics or statistical analyses.

6. ANALYSES AND SUMMARIES

6.1. Primary Endpoints

Natural log_e transformed AUC_{inf} (if data permit, otherwise AUC_{last}) of PF-07081532 administered without cyclosporine or coadministered with cyclosporine will be analyzed using a mixed effect model with treatment as a fixed effect and participant as a random

effect. Estimates of the adjusted mean differences (Test/Reference) and corresponding 90% CIs will be obtained from the models. The adjusted mean differences and 90% CIs for the differences will be exponentiated to provide estimates of the ratio of adjusted geometric means (Test/Reference) and 90% CIs for the ratios. The test treatment will be 'PF-07081532 40 mg singe dose and cyclosporine' (Period 2), which will be reported separately in comparison to the reference treatment of 'PF-07081532 40 mg singe dose without cyclosporine' (Period 1).

Natural log_e transformed AUC_{inf} (if data permit, otherwise AUC_{last}) of PF-07081532 administered without itraconazole or coadministered with itraconazole will be analyzed using a mixed effect model with treatment as a fixed effect and participant as a random effect. Estimates of the adjusted mean differences (Test/Reference) and corresponding 90% CIs will be obtained from the models. The adjusted mean differences and 90% CIs for the differences will be exponentiated to provide estimates of the ratio of adjusted geometric means (Test/Reference) and 90% CIs for the ratios. The test treatment will be 'PF-07081532 40 mg singe dose and itraconazole' (Period 3), which will be reported separately in comparison to the reference treatment of 'PF-07081532 40 mg singe dose without itraconazole' (Period 1).

6.2. Secondary Endpoints

Natural log_e transformed CCI [REDACTED] of PF-07081532 administered without cyclosporine or coadministered with cyclosporine will be analyzed using a mixed effect model with treatment as a fixed effect and participant as a random effect. Estimates of the adjusted mean differences (Test/Reference) and corresponding 90% CIs will be obtained from the models. The adjusted mean differences and 90% CIs for the differences will be exponentiated to provide estimates of the ratio of adjusted geometric means (Test/Reference) and 90% CIs for the ratios. The test treatment will be 'PF-07081532 40 mg singe dose and cyclosporine' (Period 2), which will be reported separately in comparison to the reference treatment of 'PF-07081532 40 mg singe dose without cyclosporine' (Period 1).

Natural log_e transformed CCI [REDACTED] of PF-07081532 administered without itraconazole or coadministered with itraconazole will be analyzed using a mixed effect model with treatment as a fixed effect and participant as a random effect. Estimates of the adjusted mean differences (Test/Reference) and corresponding 90% CIs will be obtained from the models. The adjusted mean differences and 90% CIs for the differences will be exponentiated to provide estimates of the ratio of adjusted geometric means (Test/Reference) and 90% CIs for the ratios. The test treatment will be 'PF-07081532 40 mg singe dose and itraconazole' (Period 3), which will be reported separately in comparison to the reference treatment of 'PF-07081532 40 mg singe dose without itraconazole' (Period 1).

6.2.1. PK Concentrations

The plasma concentrations of PF-07081532 will be listed and descriptively summarized by nominal PK sampling time and treatment. Individual participant, as well as mean and median profiles, of the plasma concentration-time data will be plotted by treatment using

DMB02-GSOP-RF02 7.0 Statistical Analysis Plan Template 31-Jan-2022

PFIZER CONFIDENTIAL

TMF Doc ID: 98.03

Page 11 of 17

actual (for individual) and nominal (for mean and median) times, respectively. Mean and median profiles will be presented on both linear and semi-log scales.

Presentations of concentrations will include:

- A listing of all concentrations sorted by participant ID, treatment and nominal time postdose. The concentration listing will also include the actual times. Deviations from the nominal time will be given in a separate listing.
- A summary of concentrations by treatment and nominal time postdose, where the set of statistics will include n, mean, median, SD, %CV, minimum, maximum and the number of concentrations above the LLQ.
- Median concentrations time plots (on both linear and semi-log scales) against nominal time postdose by treatment (all treatments on the same plot per scale, based on the summary of concentrations by treatment and time postdose).
- Mean concentrations time plots (on both linear and semi-log scales) against nominal time postdose by treatment (all treatments on the same plot per scale, based on the summary of concentrations by treatment and time postdose).
- Individual concentration time plots by treatment (on both linear and semi-log scales) against actual time postdose (there will be separate spaghetti plots for each treatment per scale).

Individual concentration time plots by participant (on both linear and semi-log scales) against actual time postdose [there will be separate plots for each participant (containing all treatments) per scale].

